6.14.4.2. Neutrophil Follow-Up

Neutrophil counts will be followed throughout the study. Patients will continue in Period 5 until their neutrophil counts have recovered.

The neutrophil follow-up analysis will be conducted on the Neutrophil Follow-Up Population defined as patients who have an absolute neutrophil count <1500 cells/ μ L (SI units: <1.5 $\times 10^9$ /L) at the last scheduled visit or early termination visit prior to entering the Post-Treatment Follow-Up Period (Period 5) and less than the patient's baseline absolute neutrophil count (that is, prior to first injection at Week 0). These patients are monitored during the Period 5 until neutrophil recovery.

Neutrophil clinical recovery is defined as an absolute neutrophil count \geq 1500 cells/ μ L (SI units: \geq 1.5 $\times 10^9$ /L) or greater than or equal to a patient's minimum absolute neutrophil count prior to first study drug injection at Week 0.

If a patient's neutrophil count has not recovered, within 12 weeks after entering the follow-up period (Visit 802), the patient will return for Visit 803 (12 weeks after Visit 802). Additional visits may be required for appropriate patient management depending upon the degree of neutropenia. If at Visit 802, a patient's has met the criteria for neutrophil recovery, the patient's participation in the study will be considered complete, unless the investigator deems additional follow-up may be necessary.

The number and percentage of patients achieving neutrophil clinical recovery will be presented by dosing regimen and week interval for Neutrophil Follow-Up Population for Post-Treatment Follow-Up Period (Period 5). The number and percentage of patients with an absolute neutrophil cell count that is at least 25%, 50%, 75%, or 100% of the patient's baseline absolute neutrophil count (that is, prior to first injection at Week 0), irrespective of absolute neutrophil minimum, will be included in the summary.

6.14.5. Vital Signs and Other Physical Findings

Analyses will be conducted on vital signs and physical characteristics including systolic blood pressure (mmHg), diastolic blood pressure (mmHg), pulse (bpm), weight (kg), BMI (kg/m²), and by-patient listing of vital signs and physical characteristics will be provided.

For vital signs and physical characteristics, the observed values at each visit (starting at baseline) and change from baseline to each scheduled visit, respectively, will be displayed in box plots for patients in P2 Main Study Safety Population who have both a baseline and at least 1 postbaseline result. These box plots will be used to evaluate trends over time and to assess a potential impact of outliers on central tendency summaries.

- The scheduled visits/measurements will be included. The unscheduled visits and the repeat measurements will be excluded.
- The following summary statistics will be included as a table below the box plot: number of patients with a baseline and at least 1 postbaseline result, mean, SD, minimum, Q1, median, Q3, and maximum.
- Data will be summarized based on original scale.

To assess the effect of administration of study drug on vital signs (blood pressures and pulse rate) among patients, at Weeks 0 and 12, vital signs will be measured before the first injection and 1 hour after the injection. The box plots will be produced for predose and postdose vital signs at Week 0 (Visit 2) and Week 12 (Visit 7).

The number and percentage of patients with treatment-emergent high blood pressure and pulse at any time for P2 Main Study Safety Population and All Ixekizumab Safety Population will be summarized. The comparisons between treatment groups will be conducted using Fisher's exact test.

- [Table RHCD.6.8](#) and [Table RHCD.6.9](#) define the limits of each category that are specified as treatment-emergent.
- All postbaseline scheduled, unscheduled and repeated measurements will be included.
- For treatment-emergent high blood pressure:
 - A treatment-emergent prehypertension is defined as a change from a value less than the low limit of prehypertension at all baseline visits to a value that is within the limits of prehypertension at any time postbaseline during the treatment period.
 - A treatment-emergent stage 1 hypertension is defined as a change from a value less than the low limit of stage 1 hypertension at all baseline visits to a value that is within the limits of stage 1 hypertension at any time postbaseline during the treatment period.
 - A treatment-emergent stage 2 hypertension is defined as a change from a value less than the low limit of stage 2 hypertension at all baseline visits to a value that is greater than or equal to the limits of stage 2 hypertension at any time postbaseline during the treatment period.
- Treatment-emergent high or low value in pulse rate:
 - A treatment-emergent high value is defined as a change from a value less than or equal to the high limit at all baseline visits to a value greater than the high limit at any time postbaseline during the treatment period.
 - Treatment-emergent low value is defined as a change from a value greater than or equal to the low limit at all baseline visits to a value less than the low limit at any time postbaseline during the treatment period.

Table RHCD.6.8. Blood Pressure Levels for Children by Age and Gender (Median Height)

Age (Year)	Hypertension Stage	Boy		Girl	
		Systolic BP (mmHg) (supine or sitting – forearm at heart level)	Diastolic BP (mmHg) (supine or sitting – forearm at heart level)	Systolic BP (mmHg) (supine or sitting – forearm at heart level)	Diastolic BP (mmHg) (supine or sitting – forearm at heart level)
6	Prehypertension	≥110 and <114	≥70 and <74	≥108 and <111	≥70 and <74
	Stage 1	≥114 and <126	≥74 and <87	≥111 and <124	≥74 and <86
	Stage 2	≥126	≥87	≥124	≥86
7	Prehypertension	≥111 and <115	≥72 and <76	≥109 and <113	≥71 and <75
	Stage 1	≥115 and <127	≥76 and <89	≥113 and <125	≥75 and <87
	Stage 2	≥127	≥89	≥125	≥87
8	Prehypertension	≥112 and <116	≥73 and <78	≥111 and <115	≥72 and <76
	Stage 1	≥116 and <128	≥78 and <91	≥115 and <127	≥76 and <88
	Stage 2	≥128	≥91	≥127	≥88
9	Prehypertension	≥114 and <118	≥75 and <79	≥113 and <117	≥73 and <77
	Stage 1	≥118 and <130	≥79 and <92	≥117 and <129	≥77 and <89
	Stage 2	≥130	≥92	≥129	≥89
10	Prehypertension	≥115 and <119	≥75 and <80	≥115 and <119	≥74 and <78
	Stage 1	≥119 and <132	≥80 and <93	≥119 and <131	≥78 and <91
	Stage 2	≥132	≥93	≥131	≥91
11	Prehypertension	≥117 and <121	≥76 and <80	≥117 and <121	≥75 and <79
	Stage 1	≥121 and <134	≥80 and <93	≥121 and <133	≥79 and <92
	Stage 2	≥134	≥93	≥133	≥92
12	Prehypertension	≥120 and <123	≥76 and <81	≥119 and <123	≥76 and <80
	Stage 1	≥123 and <136	≥81 and <94	≥123 and <135	≥80 and <93
	Stage 2	≥136	≥94	≥135	≥93
13	Prehypertension	≥120 and <126	≥77 and <81	≥120 and <124	≥77 and <81
	Stage 1	≥126 and <138	≥81 and <94	≥124 and <137	≥81 and <94
	Stage 2	≥138	≥94	≥137	≥94
14	Prehypertension	≥120 and <128	≥78 and <82	≥120 and <126	≥78 and <82
	Stage 1	≥128 and <141	≥82 and <95	≥126 and <138	≥82 and <95
	Stage 2	≥141	≥95	≥138	≥95
15	Prehypertension	≥120 and <131	≥79 and <83	≥120 and <127	≥79 and <83
	Stage 1	≥131 and <143	≥83 and <96	≥127 and <139	≥83 and <96
	Stage 2	≥143	≥96	≥139	≥96
16	Prehypertension	≥120 and <134	≥80 and <84	≥120 and <128	≥80 and <84
	Stage 1	≥134 and <146	≥84 and <97	≥128 and <140	≥84 and <96
	Stage 2	≥146	≥97	≥140	≥96
17	Prehypertension	≥120 and <136	≥80 and <87	≥120 and <129	≥80 and <84
	Stage 1	≥136 and <148	≥87 and <99	≥129 and <141	≥84 and <96
	Stage 2	≥148	≥99	≥141	≥96

Abbreviations: BP = blood pressure; mmHg = millimeters of mercury.

Source: [NIH] The Fourth report on the Diagnosis, Evaluation, and Treatment of High Blood Pressure in Children and Adolescents. Revised May 2005

Table RHCD.6.9. Categorical Criteria for Abnormal Treatment-Emergent Pulse Rate in Children and Adolescents Requiring Evaluation and Potential Intervention by a Health Care Professional

Parameter	Age (year)	Low	High
Pulse (bpm) ^a	6 - 9	<60	>150
	10 - 11	<60	>140
	12 - 14	<50	>120
	15 - 17	<50	>100

Abbreviations: bpm = beats per minute.

Source: See the Selected Reference Limits for Pulse/Heart Rate, Arterial Blood Pressure [Including Orthostasis], and Electrocardiogram Numerical Parameters for Use in Analyses of Phase 2-4 Clinical Trials guidance, located on the CV SAC Collaboration site.

^a Baseline abnormal values are defined by the value presented.

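### The treatment-emergent prehypertension row counts only readings inside a band that is mostly 3–4 mmHg wide, and no row gives the number of children with any new high blood pressure

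*SAP*

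**What the plan says.** SAP section 6.14.5 promises, for the P2 Main Study Safety Population and the All Ixekizumab Safety Population, "The number and percentage of patients with treatment-emergent high blood pressure and pulse at any time", with treatment groups compared by Fisher's exact test. It says that Tables RHCD.6.8 and RHCD.6.9 "define the limits of each category that are specified as treatment-emergent", and it admits every scheduled, unscheduled and repeat postbaseline reading.

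Three blood pressure definitions follow:

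- Prehypertension requires every baseline reading to lie under that category's low limit and a move "to a value that is within the limits of prehypertension at any time postbaseline during the treatment period".
- Stage 1 requires baseline readings below the stage 1 low limit and a move "to a value that is within the limits of stage 1 hypertension at any time postbaseline".
- Stage 2 requires baseline readings below the stage 2 limit and a move "to a value that is greater than or equal to the limits of stage 2 hypertension at any time postbaseline".

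Table RHCD.6.8 gives prehypertension and stage 1 both a lower and an upper limit. Stage 2 has only a lower one. No further row, such as any new high value, is defined.

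**The concern.** The baseline condition is one-sided, but the postbaseline condition for the two lower categories has a ceiling. A child who goes from normal straight to stage 1 readings therefore does not meet the prehypertension definition. A child who passes through two bands meets two definitions. The rows are neither nested nor mutually exclusive.

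A reader of the table will want to know how many children left the normal range on each arm. The prehypertension row looks like that number and falls short of it, and adding the rows double counts. This is a paediatric safety table, and the Period 2 Fisher test would be run on these rows.

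Other safety rules in the SAP do not work this way. High pulse (6.14.5) and high laboratory values (6.14.4) are open-ended, and ALT/AST elevations (Table RHCD.6.7) use cumulative thresholds.

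**Working it through.** The documents give no expected rate, power or variability for this analysis, so there is no planned figure to reproduce.

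**Step 1: band widths (upper minus lower limit, Table RHCD.6.8).** There are 12 ages × 2 sexes × 2 components (systolic, diastolic) = 48 cells per category.

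| Band | Width, mmHg (number of cells) |
|---|---|
| Prehypertension, all 48 | 3 (2), 4 (33), 5 (3), 6–16 (10) |
| – systolic, ages 6–12 | 3–4 in 14 of 14 |
| – systolic, ages 13–17 | 4 in 1 of 10, otherwise 6–16 |
| – diastolic, all ages | 4 in 20 of 24, 5 in 3, 7 in 1 |
| Stage 1, all 48 | 12 (25), 13 (23) |

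So 2 + 33 = 35 of 48 prehypertension bands (73%) are 3–4 mmHg wide. No stage 1 band is.

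**Step 2: the definitions applied to one child, with no assumptions.** For a boy aged 8 the systolic bands are 112 to <116 (prehypertension) and 116 to <128 (stage 1). Suppose all baseline readings are 108 and the postbaseline readings are 110, 118 and 119. No reading lies in 112 to <116, so he is not in the prehypertension row. Two readings lie in 116 to <128, so he is in the stage 1 row. Had one more reading been 113, he would be in both rows.

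**Step 3: where a skipped child goes.** The bands are contiguous, and a baseline below the prehypertension limit is also below the stage 1 and stage 2 limits. Any child newly at or above the prehypertension limit therefore meets at least one of the three definitions. Such a child can be misplaced but cannot be lost.

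**Step 4: size, by illustrative simulation of one component at a time.** Assumptions, none from the documents: usual systolic pressure 10–15 mmHg below the prehypertension limit, between-child SD 7, visit SD 5–7, 2 baseline readings. Omitted share = 1 − (in the prehypertension row) ÷ (newly at or above its low limit).

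| Systolic cell (prehypertension band) | Usual level | Visit SD | Postbaseline readings | Newly at or above limit | In row | Omitted |
|---|---|---|---|---|---|---|
| Boy 8 (4 mmHg) | −10 | 5 | 5 | 0.153 | 0.130 | 15% |
| Boy 8 (4 mmHg) | −10 | 7 | 3 | 0.163 | 0.109 | 33% |
| Girl 11 (4 mmHg) | −15 | 7 | 5 | 0.146 | 0.108 | 26% |
| Girl 11 (4 mmHg) | −15 | 5 | 7 | 0.100 | 0.088 | 12% |
| Boy 15 (11 mmHg) | −15 | 7 | 5 | 0.146 | 0.143 | 2% |

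Averaged evenly over the 24 systolic age-sex cells (usual level 12–15 mmHg below the limit, between-child SD 7–8, visit SD 5–7, 5 postbaseline readings), the omitted share is 11–21%. Over the ages with 3–4 mmHg bands alone it is 16–30%. For stage 1 it is under 2% in every scenario run.

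**Step 5: adding the rows does not help.** In the fourth scenario above (girl 11, visit SD 5, 7 readings), the three rows sum to 13.5% of children, but only 11.8% are in at least one row. Only 10.0% newly reached the prehypertension limit, and 8.8% are in the prehypertension row. The 1.8 points between 11.8% and 10.0% are children already at or above the prehypertension limit at baseline who moved to a higher category.

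**The case against.** The case against giving this much weight is fair on several counts.

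- **No child disappears.** A reader might infer that affected children are discarded. Step 3 shows they are not: each appears in a more serious row.
- **The row does not fail when the effect is large.** A reader might infer that it is least sensitive then. Under similar assumptions at 110 versus 55 children, Fisher power for the prehypertension row as written rises with the true shift: about 0.18–0.30 at +3 mmHg, 0.47–0.75 at +5 and 0.96–1.00 at +10. Only the omitted share grows, and slightly.
- **A mean shift would not go unseen.** SAP section 6.1.3.1 plans ANCOVA on continuous vital signs. Under the same assumed variances its power for +5 mmHg is about 93–99%. Box plots and a by-patient listing are also planned. Loss of power in one row of three is therefore not a measure of what the trial would miss.
- **More readings shrink the gap.** One in-band reading is enough, unscheduled and repeat readings count, and Weeks 0 and 12 add a reading 1 hour after injection. Going from 5 to 7 readings lowers 11–21% to 9–18%. With 20–28 readings (assumed), as might accrue in the All Ixekizumab Safety Population, it falls to about 2–10%.
- **Counting by band is legitimate**, and some readers will want the prehypertension band alone.

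All of this limits the harm. None of it supplies the missing count: the box plots show distributions and leave out unscheduled and repeat readings, ANCOVA compares means, and a listing neither counts nor tests.

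**Conclusion.** The point stands as a reporting defect in one safety table. Two parts follow from the text and Table RHCD.6.8 alone: the prehypertension row omits children who jump its band, and neither any row nor the sum of rows gives the number with any new high blood pressure that the section's lead sentence promises.

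The size is less certain. Roughly 10–20% missing from the prehypertension row with 5 postbaseline readings rests on assumed means, SDs and an even spread over ages, and was worked mainly on systolic pressure. It is higher at ages with 3–4 mmHg bands and close to nil for wide adolescent systolic bands. The stage 1 wording has little effect in practice. No efficacy endpoint or multiplicity-controlled test is involved. It is worth correcting because the remedy is cheap and changes a reported paediatric safety count and its comparison.

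**What to change.** In SAP section 6.14.5, define a row for children below the prehypertension low limit at all baseline visits and greater than or equal to that limit at any time postbaseline, and label it *at least prehypertension*. For consistency with stage 2, define *at least stage 1* in the same way. Either replace the two in-band rows or place the cumulative rows beside them.

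The first row then gives the number who left the normal range. A child already prehypertensive at baseline who rises further is picked up in the next row. If the sponsor means any upward move in category, a row for children meeting at least one definition should be added and labelled as such.

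The Revision History says that SAP Version 3 was approved after the primary database lock, so for Period 2 the new row should be presented as supplementary.

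The cost is a few words and about one program line, with no new data. If the rows are replaced, they become nested and a single band can no longer be read off. Adding the row instead avoids that.

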6.14.6. Standardized Growth

Weight, height, and BMI data will be merged to the Centers for Disease Control and Prevention (CDC) standard growth data (released in 2000) by age and gender in order to compare patients’ growth with the standard. Z-score and standardized percentile of weight, height, and BMI at each visit will be calculated and compared to the 2000 CDC growth charts.

The z-score and percentile calculations are based on algorithms and data provided by the National Center for Health Statistics. The details are provided in the CDC website (<https://www.cdc.gov/nccdphp/dnpao/growthcharts/resources/sas.htm>).

The following summaries will be provided for All Ixekizumab Safety Population:

- Baseline, endpoint and mean change of actual measure, z-score and standardized percentile of weight, height, and BMI will be summarized by month of ixekizumab exposure..
- Patient’s mean weight, height, and BMI standardized percentile will be plotted versus ixekizumab exposure time.

By-patient listings of actual measures, z-scores, standardized percentiles in weight height, BMI for each visit will be provided.

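### Children of every height are classified against median-height blood pressure limits although height percentiles are derived, so some are put in the wrong category; the pooled rates barely move

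*SAP*

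**What the plan says.** SAP section 6.14.5 states that Tables RHCD.6.8 and RHCD.6.9 "define the limits of each category that are specified as treatment-emergent". For blood pressure the relevant one is Table RHCD.6.8, headed "Blood Pressure Levels for Children by Age and Gender (Median Height" (the closing bracket is cut off in the quote). It has one set of systolic and diastolic limits per year of age and gender, and no height columns. A child counts as treatment-emergent stage 1, for example, on "a change from a value less than the low limit of stage 1 hypertension at all baseline visits" to a value inside the stage 1 limits at any later time. Prehypertension and stage 2 follow the same pattern, and unscheduled and repeat postbaseline readings count.

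The section says that "treatment-emergent high blood pressure and pulse at any time for P2 Main Study Safety Population and All Ixekizumab Safety Population will be summarized", and that "The comparisons between treatment groups will be conducted using Fisher's exact test".

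The next section, 6.14.6, says "Z-score and standardized percentile of weight, height, and BMI at each visit will be calculated and compared to the 2000 CDC growth charts". Of the summaries that use these percentiles it says "The following summaries will be provided for All Ixekizumab Safety Population". By-patient listings are also planned. Nothing in the SAP links the height percentile to the blood pressure limits or explains why median-height limits are enough.

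**The concern.** The table's heading concedes that its limits belong to one height group, so other heights have other limits. The plan nevertheless applies them to every child, while the input needed to do better is derived in the following section for another purpose.

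The lower categories are narrow. In Table RHCD.6.8 systolic prehypertension spans 3 to 4 mmHg for boys aged 6-12 and girls aged 6-13, so a shift of a few mmHg in the limit can move a reading a whole category. One postbaseline reading is enough to count.

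At stake is which children carry a new prehypertension or hypertension label. This matters most in the All Ixekizumab Safety Population, where there is no comparator and the percentage and the labelled children are themselves the result.

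**Working it through.** The SAP states no rate or power on this point, so there is no figure to reproduce. The text settles that the limits are median-height limits applied to all. Their effect can only be illustrated.

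**Inputs from the documents** (Table RHCD.6.8, boy aged 10, systolic): prehypertension 115 to <119 mmHg, stage 1 119 to <132 mmHg. The treatment-emergent rule is that of section 6.14.5.

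**Assumptions, not in the documents:** mean systolic pressure 102 or 107 mmHg; between-child SD 8 with within-child SD 6, or 10 with 7; 2 baseline and 5 postbaseline readings; no drug effect. The child's own limits equal the table's limits plus an offset d, and the child's usual pressure shifts by the same d.

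**Rule.** For a category with limits [L, U), a child is flagged if all baseline readings are <L and at least one postbaseline reading is ≥L and <U. The plan uses (L, U); the own-height version uses (L + d, U + d).

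**Step 1, single offsets (stage 1, 1,000,000 simulated children per scenario).**
- Own limits 3 to 5 mmHg above the table: about 12-20% flagged by the table, 8-16% by own limits.
- Own limits 3 to 5 mmHg below the table: about 3-14% by the table, 8-16% by own limits.
- d = 0: no difference.

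**Step 2, a mixed cohort.** Draw d from a normal distribution with mean 0 and SD 1.2 or 2.4 mmHg, again with 1,000,000 children per scenario. Two quantities:
- misplaced share = P(flagged by table, not by own limit) / P(flagged by table)
- pooled shift = P(flagged by table) − P(flagged by own limit)

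| Mean; SDs between/within | SD of d | Stage 1: table / own, % | Misplaced, % | Prehypertension: table / own, % | Misplaced, % |
|---|---|---|---|---|---|
| 102; 8/6 | 1.2 | 8.23 / 8.19 | 14.7 | 10.66 / 10.68 | 22.2 |
| 102; 8/6 | 2.4 | 8.45 / 8.25 | 27.5 | 10.58 / 10.69 | 38.6 |
| 102; 10/7 | 1.2 | 11.41 / 11.40 | 12.3 | 11.32 / 11.35 | 21.4 |
| 102; 10/7 | 2.4 | 11.44 / 11.40 | 23.1 | 11.19 / 11.39 | 37.5 |
| 107; 8/6 | 1.2 | 14.77 / 14.84 | 13.5 | 14.85 / 14.97 | 21.2 |
| 107; 8/6 | 2.4 | 14.66 / 14.82 | 24.8 | 14.62 / 15.04 | 36.4 |
| 107; 10/7 | 1.2 | 16.21 / 16.28 | 11.7 | 13.75 / 13.78 | 21.1 |
| 107; 10/7 | 2.4 | 16.07 / 16.27 | 21.7 | 13.48 / 13.79 | 36.3 |

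Misplaced flags are about 12-28% for stage 1 and 21-39% for prehypertension. The largest pooled shift is 15.04 − 14.62 = 0.42 points. The two fit together because a similar share of own-limit flags is missed by the table (12-26% for stage 1, 21-39% for prehypertension), so gains and losses nearly cancel.

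**Step 3, an off-centre cohort.** With the mean of d at +1 or −1 mmHg, the stage 1 percentage moves by about 1 to 1.4 points in most scenarios (0.5 to 1.5 over all of them), up or down with the sign of d. Prehypertension moves by at most about 1.1 points.

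Steps 2 and 3 draw the offset in the limit, not the height, so they do not depend on whether limits rise or fall with height.

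**The case against.** The strongest case against is that almost nothing reported would change. No blood pressure summary by height is planned, so errors in tall and short children never appear separately, and in the pooled table they cancel. This stands. A reader might infer that the reported percentage in the uncontrolled population is materially distorted. The documents do not support that: it would need a cohort whose heights are off-centre, and they do not show one.

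A reader might also infer that tall children are over-flagged and short children under-flagged. The documents do not support that either. The heading shows only that limits depend on height; the sign and size stand in an outside report that the SAP cites but does not reproduce.

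Nor does the plan bias the randomized comparison. The same limits apply in both arms and at baseline, so the error is expected to be non-differential. It could cost some sensitivity, but no loss of power has been quantified.

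The narrow-band argument is limited to younger children. Stage 1 systolic bands are 12 to 13 mmHg wide. From age 12 in boys and 13 in girls the prehypertension systolic floor is a constant 120 mmHg, and whether it varies with height is not shown.

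Finally, the simplification is declared in the table heading. Period 2 box plots and by-patient listings show the raw values, and the blood pressure deviation D12 in Table RHCD.6.12 does not cite this table.

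What survives is classification of the individual child. Cancellation in the total does not make the right children carry the label, and the SAP gives no reason for leaving height out.

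**Conclusion.** The point holds as a minor, low-cost improvement. Children away from median height can be put in the wrong blood pressure category. The misplaced shares of 12-28% and 21-39%, the pooled shift below 0.5 points, and the off-centre shift of about 1 to 1.4 points for stage 1 all rest on the assumed offsets and pressure distribution, on pressure tracking the child's own limit, and on one age and gender taken as the example. They show a plausible scale and are not estimates for this cohort. No bias toward ixekizumab or placebo follows.

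**What to change.** For the treatment-emergent blood pressure summaries, take the limits for the child's own height percentile from the source already cited under Table RHCD.6.8, keyed to the percentile in section 6.14.6 and using the last height on or before the reading. Apply this to the All Ixekizumab Safety Population. For Period 2, report it as a supportive analysis beside the median-height table, because the SAP's revision history places this version after the primary (12-week) database lock. Category names and the treatment-emergent rule stay unchanged.

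The cost is a larger lookup table that no longer fits on a page. Height percentiles must also be derived for the Period 2 placebo arm, since section 6.14.6 plans its summaries only for the All Ixekizumab Safety Population. Heights must be carried forward where none was measured at the visit: section 6.8.1 takes baseline height from Visit 1, and the documents at hand do not show the schedule of later height measurements. No new visits or patients should be needed.
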